6.2.3 Follow-up Visits

Not applicable

6.2.4 Final Evaluation

- Post-Clinic Visit up to 60 days (2 months post visit):
 - Research staff at each clinical site will identify and confirm documentation of the PPC visit in the EHR. Currently available reporting tools will be used to automate extraction of as much of this information as possible, and further automation of data collection using the NLP model will be implemented as available.
 - Research staff will record any Adverse Events experienced by the patient as applicable.
- Post-Clinic Visit up to 90 days (3 months post visit):
 - Conduct semi-structured interviews with some PLWDM, Care Partners and Clinicians (PEP Talks section 5.2)
 - Adverse Events

7 SAFETY ASSESSMENTS

Participant safety will be monitored, however, due to the nature of the study, the risks encountered during the PPC conversation are no greater than those expected during a routine clinic visit. Patient safety will be monitored at the clinician level since the conversation takes place during a routine clinic visit.

The Principal Investigator (PI) will be responsible for ensuring participants' safety on a daily basis. Quarterly meetings between study sites will review any safety concerns and will review coordination of safety information between sites. In addition, the NIA IMPACT Collaboratory Safety Officer (SO) will oversee all data and safety monitoring activities for this study. The SO will be determined by NIA. The SO will act in an advisory capacity to the NIA Director to monitor participant safety, to evaluate the progress of the study, and to review procedures for maintaining the confidentiality of data, the quality of data collection, management, and analyses. Advarra IRB will conduct the ethical review required for the protection of human subjects. NIA PO, in consultation with the SO, will make a determination regarding the level and format of data and safety

monitoring this study requires, i.e. how often reporting is required.

Refer to the [IMPACT Collaboratory DSMB Charter](#) for details.

There are three potential risks to participation in the study. First, a past study of the PPC intervention found that there is a slightly increased risk of individuals receiving the intervention to be prescribed psychotropic medications. Psychotropic medications can include antidepressants and antipsychotics, the latter which has been overprescribed and inappropriately prescribed to individuals with dementia. To address this concern, the training protocol includes education on risks of antipsychotics. Second, there is the risk of potential breach of confidentiality. Third, individuals who participate in semi-structured interviews following the PPC conversation, may encounter questions that they would prefer not to answer. If this occurs, the participant can decline to respond. Additionally, participants may choose not to participate in an interview. There will be no penalty for providers not participating and all patients and care partners will be informed that choosing not to participate will not affect their clinical care.

7.1 Specification of Safety Parameters

Not applicable

7.2 Methods and Timing for Assessing, Recording, and Analyzing Safety Parameters

All adverse events, unanticipated problems and potential risks will be monitored and collected on an ongoing basis, and throughout the study by the research staff. Events, which are anticipated because they are related to the worsening or advancing of the underlying disease, or symptoms related to the disease, will be monitored through patient or care partner report. Events related to any patient, care partner, and provider loss of privacy or confidentiality, or related to fatigue, frustration, or distress related to completing the intervention will be assessed by the research staff via monitoring of the delivery of the study protocols and procedures within the EHR and by patient and care partner reports to the research staff.

Adverse Events and Serious Adverse Events

Adverse Event (AE): Any untoward or unfavorable medical occurrence in a clinical research study participant, including any abnormal sign (e.g. abnormal physical exam or laboratory finding), symptom, or disease, temporally associated with the patient's involvement in the research, whether or not considered related to participation in the research.

Serious Adverse Event (SAE): Any adverse event that:

- Results in death
- Is life threatening, or places the participant at immediate risk of death from the event as it occurred
- Requires or prolongs hospitalization
- Causes persistent or significant disability or incapacity
- Results in congenital anomalies or birth defects
- Is another condition which investigators judge to represent significant hazards

Unanticipated Problem (UP) Definition: any incident, experience, or outcome that meets all of the following criteria:

- unexpected, in terms of nature, severity, or frequency, given (a) the research procedures that are described in the protocol-related documents, such as the IRB-approved research protocol and informed consent document; and (b) the characteristics of the study population;
- related or possibly related to participation in the research;
- suggests that the research places participants or others at a greater risk of harm (including physical, psychological, economic, or social harm) than was previously known or recognized.

For all participants, adverse events will be collected starting at enrollment and continue until after the participant has completed the study.

Unanticipated problems, that do not meet the definition of an adverse event, will be documented in a study log that will be stored in a secure electronic folder behind the university fire wall. Details in the log may include participant study ID, date that the problem was reported or discovered by the study, a description of the problem, and a corrective plan and measures to prevent reoccurrence.

Adverse events associated with this study are likely to be infrequent. The IMPACT Collaboratory adverse event form will be used by research staff to report all adverse events caused by the intervention.

AEs for this study include: Some participants may feel increased stress or anxiety while participating in the intervention. Breach of confidentiality would also constitute an AE.

SAEs for this study include: PLWDM have an increased risk of hospitalization, nursing home admission, and death at baseline and these SAEs may occur during the course of the study.

7.2.1 Reporting Procedures

The content of the data and safety monitoring report will include study status, recruitment, enrollment, and retention information and participant descriptive information. Safety and quality information will be reported using study quality reports for Co-PIs that will contain:

- Summary of adverse events, participant descriptive information, and an explanation of how each event was handled,
- Summary of complaints and how each complaint was handled,
- Subject retention, including the number and reasons of participant withdrawals,
- Summary of protocol violations and how each was handled. Reports will be submitted to the IRB on an as-needed basis.

All adverse events will be initially judged by the PI ([name]) based on three criteria:

1. expectedness (expected, unexpected),
2. relatedness to participation in the study (definitely related, possibly related, not related), and
3. severity (mild, moderate, severe).

These judgments will be circulated to the study team and reported to the Program Official as noted below.

- All **adverse events that are serious (SAE) and unexpected** (i.e., have not been previously reported for the study's intervention) will be reported to the IMPACT Collaboratory Regulatory and Data Team Leader ([name]), NIA IMPACT Collaboratory PO ([name]), and the IMPACT Collaboratory project's Safety Officer (SO) within 48 hours of the study's knowledge of SAE.
 - Only those adverse events that are serious (SAE), unexpected, **and related to the intervention** must also be reported to Advarra IRB. Unexpected and **unrelated** SAEs will be reported to Advarra IRB on a case-by-case basis if requested by the IMPACT Collaboratory project's Safety Officer (SO) or NIA IMPACT Collaboratory PO.
- All deaths will be reported to IMPACT Collaboratory Regulatory and Data Team Leader ([name]), NIA IMPACT Collaboratory PO ([name]), and the IMPACT Collaboratory project's Safety Officer (SO) within 24 hours of study's knowledge of death.
 - Advarra IRB does not require the specific reporting of death outside of the SAE reporting requirement above, but they will be notified on a case-by-case basis if requested by the IMPACT Collaboratory project's Safety Officer (SO) or NIA IMPACT Collaboratory PO.
- All unanticipated problems (UPs) will be reported to the IMPACT Collaboratory Regulatory and Data Team Leader ([name]), Advarra IRB, NIA IMPACT Collaboratory PO ([name]), and the IMPACT Collaboratory project's Safety Officer (SO) within 48 hours of the study's knowledge of the event.
- The summaries of all previously reported unexpected and related SAEs, deaths, and UPs, as well as all other SAEs and AEs will be reported to IMPACT Collaboratory Regulatory and Data Team Lead ([name]), Advarra IRB, NIA IMPACT Collaboratory PO ([name]), and the IMPACT Collaboratory project's Safety Officer (SO) at a minimum every 6

months, or at a frequency requested by the IMPACT Collaboratory project's Safety Officer (SO) or NIA IMPACT Collaboratory PO.

Severity of Event

- **Mild:** Awareness of signs or symptoms, but easily tolerated and are of minor irritant type causing no loss of time from normal activities. Symptoms do not require therapy or a medical evaluation; signs and symptoms are transient.
- **Moderate:** Events introduce a low level of inconvenience or concern to the participant and may interfere with daily activities, but are usually improved by simple therapeutic measures; moderate experiences may cause some interference with functioning
- **Severe:** Events interrupt the participant's normal daily activities and generally require systemic drug therapy or other treatment; they are usually incapacitating

Expectedness of Event

- **Unexpected** - nature or severity of the event is not consistent with information about the condition under study or intervention in the protocol, consent form, product brochure, or investigator brochure.
- **Expected** - event is known to be associated with the intervention or condition under study.

Unexpected events will be subject to expedited reporting requirements as described in the [NIA Guidance on Clinical Trials](#).

Relationship to Study Intervention

- **Definitely Related:** The adverse event is clearly related to the investigational agent/procedure – i.e. an event that follows a reasonable temporal sequence from administration of the study intervention, follows a known or expected response pattern to the suspected intervention, that is confirmed by improvement on stopping and reappearance of the event on repeated exposure and that could not be reasonably explained by the known characteristics of the subject's clinical state.
- **Possibly Related:** An adverse event that follows a reasonable temporal sequence from administration of the study intervention follows a known or expected response pattern to the suspected intervention, but that could readily have been produced by a number of other factors.
- **Not Related:** The adverse event is clearly not related to the investigational agent/procedure - i.e. another cause of the event is most plausible; and/or a clinically plausible temporal sequence is inconsistent with the onset of the event and the study intervention and/or a causal relationship is considered biologically implausible.

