8 INTERVENTION DISCONTINUATION

This is a one-year pilot study to establish feasibility with low anticipated risk. If there were unanticipated serious adverse events that were possibly or probably related to the study, we would review with the institutional review board and consider discontinuation.

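### Both related grades in Section 7.2.1 require a response pattern already known or expected, so a serious event of a new kind can fit no grade and miss the automatic IRB report

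*Protocol*

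**What the plan says.** Protocol Section 7.2.1 has the PI make the initial judgement of every adverse event on expectedness, severity and relatedness. Relatedness has three grades:

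- *Definitely Related*: plausible timing, a response already known or expected, no reasonable explanation in the patient's own clinical state, and an event "that is confirmed by improvement on stopping and reappearance of the event on repeated exposure".
- *Possibly Related*: an event that "follows a reasonable temporal sequence from administration of the study intervention follows a known or expected response pattern to the suspected intervention", although other factors could readily have produced it.
- *Not Related*: "The adverse event is clearly not related to the investigational agent/procedure". The text explains this as another cause being most plausible, timing that does not fit, or biological implausibility.

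*Unexpected* is described in two ways in the same section. The expectedness definition says that the "nature or severity of the event is not consistent with information about the condition under study or intervention" set out in the protocol, consent form or brochures. The reporting rule instead glosses it as an event not yet reported for this intervention.

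Three rules then combine unexpectedness with relatedness:

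1. A serious event that is unexpected and related to the intervention "must also be reported to Advarra IRB" (Section 7.2.1).
2. An unanticipated problem must be unexpected in nature, severity or frequency, must be "related or possibly related to participation in the research", and must point to a greater risk of harm than was recognised (Section 7.2). It goes to the IRB within 48 hours (Section 7.2.1).
3. Section 8 begins "If there were unanticipated serious adverse events that were possibly or probably related to the study" and says that the team would then review with the IRB and consider discontinuation.

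**The concern.** An expedited rule for unexpected and related events exists to catch a harm nobody foresaw. Here the relatedness grades ask, as a condition of being called related, that the event match a pattern already known or expected. For an event new in kind, the test for *unexpected* and the test for *related* pull against each other. The top grade also asks for evidence from stopping and re-exposure, which makes sense for a drug taken repeatedly but not for a conversation held around one clinic visit.

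Patients enter under a waiver of consent justified by minimal risk (Section 11.2). Prompt, automatic notice to the IRB of a new and possibly related harm therefore matters more here than in a study where each patient has consented.

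**Working it through.** No arithmetic applies. The check is whether each way of being unexpected can hold together with each relatedness grade, and which rules then apply.

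**Step 1: can the grades be applied to this intervention?** PPC has two steps. The facilitator step takes place 1-2 weeks before the visit or in tandem with it, and the clinician step takes place at Visit 1, Day 0 (Sections 5.1 and 6.1). No repeat exposure is scheduled. *Definitely Related* is therefore unattainable in practice. *Possibly Related* and *Not Related* carry no stopping or re-exposure condition and can be applied. So one grade of three is affected.

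**Step 2: cross the routes to unexpectedness with the grades.** Take an event with plausible timing, no more plausible cause and no biological implausibility.

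| Unexpected in | Definitely Related | Possibly Related | Not Related |
|---|---|---|---|
| Nature | Closed: pattern and re-exposure | Generally closed: pattern | Closed: not clearly unrelated |
| Severity (known kind) | Closed in practice: re-exposure | Open | Closed: not clearly unrelated |
| Frequency (unanticipated problems only) | Closed in practice: re-exposure | Open | Closed: not clearly unrelated |

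The first row has no usable grade, although the PI must assign one. The kinds of effect or event that the protocol itself associates with the intervention or the study are stress or anxiety, breach of confidentiality and psychotropic prescribing (Sections 7 and 7.2). A serious event outside that short list is the case at issue.

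**Step 3: carry the rows into the rules.**

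- *IRB report of a serious event.* The nature route is generally closed. The severity route is open only if *related* includes *possibly related*, which Section 7.2.1 does not say. If it means *definitely* only, this rule is effectively closed. Under the gloss of not yet reported for the intervention, an event of a known kind may not count as unexpected at all, which narrows the severity route further.
- *Unanticipated problem.* If the 7.2.1 grades are used, two of three routes (severity and frequency) stay open. Problems that are not adverse events are logged separately (Section 7.2) and do not pass through the adverse-event grades.
- *Section 8 review.* If the same grades are used, the severity route is open through *possibly*. *Probably* is not one of the three grades, and *definitely*, which is, does not appear.

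**Step 4: what reaches oversight without a related grade?** Every serious unexpected event goes to the Collaboratory's regulatory lead, the NIA Program Official and the Safety Officer within 48 hours. Every death reaches them within 24 hours. The Safety Officer or Program Official may ask for unrelated unexpected serious events to go to the IRB. All other events are summarised, IRB included, at least every 6 months (all Section 7.2.1).

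**The case against.** The strongest reply is that little is lost. Independent oversight sees every unexpected serious event within two days whatever its grade, the PI's grading is only initial, and the Safety Officer or Program Official can send the event on to the IRB. That stands as a limit on the consequence. It does not close the gap: for this event, an automatic IRB report becomes one made on request or a summary that may come up to six months later.

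A second reply is that the tests are not strictly exclusive. An event absent from the listed documents could still follow a pattern that a clinician would expect, such as a serious reaction to a distressing discussion. Distress at the facilitator step that settles and returns at the clinician step might even meet the re-exposure condition. This is fair, and is why the point says *generally* and *in practice*.

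A third reply is that neither the unanticipated-problem definition nor Section 8 cites the 7.2.1 grades, and each has its own relatedness wording. That also stands. The effect on those two rules is conditional on the same grades being used.

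A reader might go further and infer that the scale cannot be used at all for a conversation, or that the three rules can hardly ever operate. The documents do not support either reading: two of the three grades can be applied, and the severity, frequency and non-adverse-event routes remain. Nor is Section 8 the only way to stop the study. The Safety Officer may recommend termination (Section 7.3), and the IRB, NIA and other bodies may discontinue the study (Section 11.4).

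**Conclusion.** The point holds in a limited form. Section 7.2.1 states a rule that leaves a serious event unexpected in nature, with plausible timing and no better explanation, without a usable grade. Such an event can miss the automatic IRB report and, if the same grades are used there, the unanticipated-problem report and the Section 8 review. What is lost is prompt, automatic IRB notice and possibly the Section 8 review. Early sight of the event by the Safety Officer and Program Official is not lost.

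The conclusion assumes that the grades are applied as written and that no repeat exposure occurs beyond the two scheduled steps. The documents give no rates for such events, so how often this would happen cannot be stated.

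A reader might also infer that a clean safety result from this pilot would be used to support a consent waiver for the full trial. No section says so, and the progression criteria in Section 9.4 contain no safety criterion, so the point does not rest on it.

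**What to change.** In Section 7.2.1:

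- Drop the stopping and re-exposure condition, and drop the known-or-expected pattern condition, as requirements for a related grade.
- Define *Possibly Related* by plausible timing and a reasonable possibility that participation contributed, even where other causes exist.
- Make *Possibly Related* the default for an event that fits no other grade.
- State that *related* in the IRB rule for serious events includes *possibly related*.
- Reconcile the two descriptions of *unexpected*, and reconcile grading against study participation with grading against the intervention.

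Reconcile the relatedness terms in Section 8 with the three-grade scale.

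The cost is a wording amendment and, probably, a few more events graded *possibly related* and sent to the IRB. No data collection changes.

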7.2.2 Follow-up for Adverse Events

The occurrence of an adverse event (AE) or serious adverse event (SAE) may come to the attention of research staff during EHR review of documentation of clinic visits, or during semi-structured participant interviews.

All AEs including local and systemic reactions not meeting the criteria for SAEs will be captured on the appropriate case report form (CRF) and/or the IMPACT Collaboratory AE form, as necessary. Information to be collected includes event description, time of onset, qualified medical professional's assessment of severity, relationship to study product (assessed only by those with the training and authority to make a diagnosis), and time of resolution/stabilization of the event. All AEs occurring while on study must be documented appropriately regardless of relationship. All AEs will be followed to adequate resolution.

Any medical condition that is present at the time that the participant is screened will be considered as baseline and not reported as an AE. However, if the study participant's condition deteriorates at any time during the study, it will be recorded as an AE.

Changes in the severity of an AE will be documented to allow an assessment of the duration of the event at each level of severity to be performed. AEs characterized as intermittent require documentation of onset and duration of each episode.

7.3 Safety Monitoring

The NIA Guidelines on Data and Safety Monitoring generally require that a NIA-appointed Data and Safety Monitoring Board or Safety Officer monitor clinical trials. Please see the [Data and Safety Monitoring Guidelines](#). This study has been assigned to a Safety Officer only.

The study PI will present their safety reports at the intervals described below. Safety reports will be provided to the SO and NIA PO.

Data will be presented in a blinded manner in SO reports. SO reports, data and discussion are confidential. Participant identities will not be known to the SO.

For the study, the frequency of DSM will proceed as follows:

1. Prior to the start of participant enrollment and data collection, the study PI must submit a DSMP for approval by the SO and/or the NIA PO;
2. Six months after the initiation of participant enrollment and/or data collection, the study PI must provide a DSM report to the SO, through submission to the IMPACT IRB and Regulatory Team. This interim report will be reviewed by the SO to determine whether there are any human subjects or data safety concerns; and
3. At the end of the study, the PI must submit a final DSM report to the SO, through submission to the IMPACT IRB and Regulatory team.

The SO will sign a Conflict of Interest Statement which includes current affiliations, if any, with pharmaceutical and biotechnology companies (e.g., stockholder, consultant), and any other relationship that could be perceived as a conflict of interest related to the study and / or associated with commercial interests pertinent to study objectives.

Safety Officer

[name], MSc

Geriatric Medicine Specialist, Hebrew SeniorLife

[name] is a geriatric medicine specialist who specializes in chronic wound care and technology. She has a fellowship in chronic wound healing and uses evidence-based care to develop methods of prevention and management of pressure ulcers. [name] previously served as the Chair of the Institutional Review Board at Hebrew Senior Life.

SO Responsibilities

The role of the SO is described in the [IMPACT Collaboratory DSMB Charter](#).

A detailed list of SO responsibilities includes:

- Review the research protocol, informed consent documents and plans for data safety and monitoring;
- Recommend subject recruitment be initiated after receipt of a satisfactory protocol;
- Evaluate the progress of the trial, including periodic assessments of data quality and timeliness, recruitment, accrual and retention, participant risk versus benefit, performance of the trial sites, and other factors that can affect study outcome;
- Consider factors external to the study when relevant information becomes available, such as scientific or therapeutic developments that may have an impact on the safety of the participants or the ethics of the trial;
- Review study performance, make recommendations and assist in the resolution of problems reported by the PI;
- Protect the safety of the study participants;
- Report to NIA on the safety and progress of the trial;
- Make recommendations to the NIA and the PI concerning continuation, termination or other modifications of the trial based on the observed beneficial or adverse effects of the treatment under study;
- If appropriate, review interim analyses in accordance with stopping rules, which are clearly defined in advance of data analysis and have the approval of the DSMB;
- Ensure the confidentiality of the study data and the results of monitoring; and,
- Assist the NIA by commenting on any problems with study conduct, enrollment, sample size, and/or data collection.

